9.1.7.3 Performance Site

RNA will be isolated in the [name] laboratory of the Mayo Clinic Cancer Center. Library construction will take place in the Gene Expression Core of the Mayo Clinic Genome Research Facility; and sequencing of the library will take place in the Sequencing Core of the Mayo Clinic Genome Research Facility.

9.1.7.4 Data Supporting the Degree of Biomarker “Fit for Purpose”

Results currently submitted for publication (14) document the reproducibility of the assay as well as its ability to identify changes in the transcriptome that result from alterations in transcription factors as a consequence of treatment of human ALL cell lines with mTOR dual inhibitors.

9.1.7.5 Justification of the Number of Patients and Specimens

The purpose of the assay is to determine whether MLN0128 (TAK-228) induces transcriptional changes in ALL cells *in situ* that reflect its mechanism of cytotoxicity at clinically achievable concentrations. This will be the first opportunity to assess changes in the transcriptome in clinical ALL after treatment with an mTOR dual inhibitor, so the extent and frequency of transcriptional changes cannot be estimated from precedent data.

9.2 Laboratory Correlative Studies

9.2.1 MLN0128 (TAK-228) Pharmacokinetics – CSF

9.2.1.1 Patient Considerations

Patients participating in this study will have intrathecal (IT) chemotherapy as clinically indicated care within 7 to 10 days of starting study treatment. If possible, collect up to a 2 mL sample of CSF prior to the infusion of the IT chemotherapy. If a patient has another clinically indicated IT chemotherapy performed at any subsequent time in the study, collect an additional 2 mL sample of CSF prior to the infusion of the IT chemotherapy, if possible.

9.2.1.2 CSF Collection Schedule

Collect up to 2 mL of CSF prior to the infusion of the IT chemotherapy within 7 to 10 days of starting study treatment and prior to any subsequent clinically indicated IT chemotherapy performed at any time during the study if possible.

9.2.1.3 Handling of Specimens

At Mayo Clinic Rochester only: Transport CSF sample on ice to [name] lab.

For all other sites: Transfer CSF sample to cryovial and freeze at -80° C. Ship with PK serum samples.

9.2.2 MLN0128 (TAK-228) Pharmacokinetics – Plasma

9.2.2.1 Patient Considerations

Patients participating in this study will be asked to provide blood samples during Cycle 1 of treatment. The morning dose of MLN0128 (TAK-228) must not be given until after pretreatment blood draw.

9.2.2.2 Blood Collection Schedule

Blood samples (6 ml) will be drawn in green top sodium heparin tubes 30 minutes before drug administration on Days 1, 2 and 8, and at the following times after administering the oral dose on Day 1 and 8: 30 min, 1 hr, 2 hrs, 3 hrs, 4 hrs, and 8 hrs. Thus, 15 samples will be collected for a total of 90 ml whole blood. Note that the windows for the pk samples are \pm 10 min for the 30 minutes pre-drug sample; \pm 5 minutes for the 30 minute and 1 hour post-drug samples; \pm 10 min for 2 hours post-drug sample and \pm 15 min for the 3, 4 and 8 hour post-drug samples. It is more important to record time accurately than to perform the blood drawn exactly at the scheduled time.

Note: The physical exam and labs performed on Cycle 1 Day 1 may be performed the day prior in order to begin the pharmacokinetic sample collection early enough on Cycle 1 day 1 that an 8 hour pk sample is possible. If an 8 hour pk draw is not possible, please collect a 7 hour or a 7 $\frac{1}{2}$ hour sample and note the timepoint on the label of the tube and a collection draw worksheet.

Please complete the pk sample blood draw list in Appendix D and include a copy with the samples at shipment.

9.2.2.3 Handling of Specimens

Collect blood samples in sodium heparin (green-top) tubes and immediately cool in an ice water bath. Isolate plasma within 20 minutes of collection.

Blood will be subjected to centrifugation (2,000 rpm for 10 minutes) in a refrigerated centrifuge kept at 4°C. Following centrifugation, plasma aliquots of at least 2 ml each should be transferred to 4 mL plastic cryovials, capped and immediately frozen

at -70°C.

Tube labels must contain the following data: patient identification code, date, draw timepoint and actual time of draw. Please complete the pk sample blood draw list in Appendix D and include a copy with the samples at shipment. with the samples.

9.2.2.5 Site(s) Performing the Pharmacokinetic Study

Samples will be analyzed in the Pharmacology Core of the Mayo Clinic Cancer Center, which has developed validated assays for over 85 separate anticancer drugs during the course of its existence.

10. STUDY CALENDAR

Baseline evaluations are to be conducted within 1 week prior to start of protocol therapy. Scans and x-rays must be done \leq 4 weeks prior to the start of therapy. In the event that the patient's condition is deteriorating, laboratory evaluations should be repeated within 48 hours prior to initiation of the next cycle of therapy. After C1D15, a window of + 7 days for study procedures is permitted.

Mayo Clinic Rochester only: Research blood for pharmacodynamic assays ^{h, R}	X		X											
a:	Albumin, alkaline phosphatase, total bilirubin, bicarbonate, BUN, calcium, chloride, creatinine, fasting glucose, LDH, phosphorus, potassium, total protein, SGOT [AST], SGPT [ALT], sodium, uric acid.													
b:	Serum pregnancy test (women of childbearing potential).													
c:	Aspirate only for research assay is collected.													
d:	1 month after end of treatment													
e:	CSF sample collected during clinically indicated intrathecal chemotherapy for pk analysis if possible. If subsequent clinically indicated intrathecal chemotherapy is performed, a CSF sample is requested if possible. Collect up to 2 mL if possible, transfer to a cryovial and freeze at -80° C. Ship to [name] lab with the blood pk samples.													
f:	Blood draws for pk's are collected 30 minutes (\pm 10 minutes) before study drug administration on Days 1, 2 and 8, and at the following times after study drug on Day 1 and 8: 30 minutes (\pm 5 minutes), 1 hour (\pm 5 minutes), 2 hours (\pm 10 minutes), 3 hrs, 4 hrs, and 8 hours (all \pm 15 minutes). It is more important to record time accurately than to perform the blood draw exactly on time.													
g:	Cycle 1 Day 1 physical exam and labs may be performed the day prior to Cycle 1 Day 1 in order to start the pharmacokinetic samples collection early on Cycle 1 Day 1.													
h:	Blood draws for pharmacodynamics are collected anytime prior to the first dose of MLN0128 (TAK-228) and at Cycle 1 Day 2 with the PK draw. R: Research funded													

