A death on INK128-001 due to ventricular arrhythmia and cardiac arrest was assessed as possibly related to MLN0128 (TAK-228). After discussion with the FDA, study C31002, a phase 1 single-arm study to evaluate the effect of a single dose of 40 mg MLN0128 (TAK-228) on the QT/QTc interval was initiated in patients with advanced solid tumors. After completing the per-protocol PK/ECG/cardiac contractility monitoring, the patients continued MLN0128 (TAK-228) 30 mg QW with continued cardiac monitoring. The study results showed that treatment with MLN0128 (TAK-228) was not associated with clinically meaningful effects on the overall electrocardiographic safety profile, and that ECHO/MUGA at screening is not required on MLN0128 (TAK-228) trials. Takeda and CTEP have agreed that ECG monitoring should be performed on patients prior to entering MLN0128 (TAK-228) trials, at the time of completing treatment with MLN0128 (TAK-228), and periodically during the trial when clinically appropriate.

In INK128-002, which was reported by Ghobrial *et al.* (17) MLN0128 (TAK-228) was administered orally to 37 patients in two different schedules, either daily or three days on/four days off every week schedule with 28-day cycles. The maximum tolerated dose (MTD) was 6 mg for the daily schedule and was not defined in the 3 days on/four days off schedule. Common side effects included nausea (56%), fatigue (49%), hyperglycemia (38%), thrombocytopenia (36%), diarrhea (28%), anorexia (23%), emesis (23%), stomatitis (21%), anemia (21%), and constipation (18%). 27% discontinued drug due to an adverse event. Among 27 patients evaluable for confirmed responses, 1 multiple myeloma patient (7 mg QD) achieved a major response lasting 2 months, and 13 myeloma patients (2 at 2 mg QD, 4 each at 4 mg QD and 7 mg QD, 2 at 9 mg QDx3d QW, and 1 at 12 mg QDx3d QW) and 2 Waldenstrom's macroglobulinemia patients (at 6 mg QD and 9 mg QDx3d QW) had stable disease.

Subsequent experience with the daily schedule has indicated that MLN0128 (TAK-228) at 6 mg/day is intolerable for prolonged administration in some patients ([name], personal communication). Accordingly, the recommended phase 2 dose is 5 mg/day for daily administration.

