Recommended management: Loperamide antidiarrheal therapy Dosage schedule: 4 mg at first onset, followed by 2 mg with each loose motion until diarrhea-free for 12 hours (maximum dosage: 16 mg/24 hours) Adjunct anti-diarrheal therapy is permitted and should be recorded when used.	

Hyperglycemia	Management/Next Dose for MLN0128 (TAK-228)
≤ Grade 1	No change in dose. Optimize blood sugar control. *
Grade 2	No change in dose. Optimize blood sugar control.
Grade 3 Asymptomatic	No change in dose. Optimize blood sugar control.
Grade 3 Symptomatic or >7 days on therapy	Hold** until < Grade 2. Resume at one dose level lower.
Grade 4	Off protocol therapy
* If medical therapy is needed, metformin is preferred unless contraindicated. Sulfonylurea can be added if metformin does not control blood glucose level. If this fails to bring it to ≤ G1 within 1 month, then oral hypoglycemics can be stopped and insulin used.	
**Patients requiring > two dose reductions should go off protocol therapy.	
Hyperglycemia will be based on fasting glucose level.	

Thrombocytopenia and neutropenia	Management/Next Dose for MLN0128 (TAK-228)
≤ Grade 1	No change in dose
Grade 2	Hold until ≤ Grade 1. Resume at same dose level.
Grade 3	Hold* until ≤ Grade 1. Resume at one dose level lower
Grade 4	Off protocol therapy
This dose modification for thrombocytopenia and neutropenia only pertains to	

Thrombocytopenia and neutropenia	Management/Next Dose for MLN0128 (TAK-228)
	patients in remission. Thrombocytopenia and neutropenia will not be considered dose limiting during remission induction.
	*Patients requiring a delay of >4 weeks if related to MLN0128 (TAK-228) should go off protocol therapy. This only will be counted if patients are in remission (CR).
	**Patients requiring > two dose reductions should go off protocol therapy.

Non-hematological toxicity:

Non-hematological toxicities of fatigue, electrolyte abnormalities and abnormal liver function tests, including bilirubin, transaminases and alkaline phosphatase will only require dose modification if they are likely or definitely related to MLN0128 (TAK-228) and persist more than 7 days. Neutropenic fever and infectious toxicities are only counted for if patients achieve remission and then develop these adverse events.

Non-Hematological Toxicity

Event	Management/Next Dose for MLN0128 (TAK-228)
≤ Grade 1	No change in dose
Grade 2	Hold until ≤ Grade 1. Resume at same dose level.

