7.1.1 CAEPR for MLN0128 (TAK-228)

Comprehensive Adverse Events and Potential Risks list (CAEPR) for MLN0128 (TAK-228) (INK128, NSC 768435)

The Comprehensive Adverse Events and Potential Risks list (CAEPR) provides a single list of reported and/or potential adverse events (AE) associated with an agent using a uniform presentation of events by body system. In addition to the comprehensive list, a subset, the Specific Protocol Exceptions to Expedited Reporting (SPEER), appears in a separate column and is identified with bold and italicized text. This subset of AEs (SPEER) is a list of events that are protocol specific exceptions to expedited reporting to NCI (except as noted below). Refer to the 'CTEP, NCI Guidelines: Adverse Event Reporting Requirements'
http://ctep.cancer.gov/protocolDevelopment/electronic_applications/docs/aeguidelines.pdf for further clarification. *Frequency is provided based on 252 patients.* Below is the CAEPR for MLN0128 (TAK-228)(INK128).

NOTE: Report AEs on the SPEER **ONLY IF** they exceed the grade noted in parentheses next to the AE in the SPEER. If this CAEPR is part of a combination protocol using multiple investigational agents and has an AE listed on different SPEERs, use the lower of the grades to determine if expedited reporting is required.

Version 2.2, April 26, 2016

Adverse Events with Possible Relationship to MLN0128 (TAK228) (CTCAE 4.0 Term) [n= 311]			Specific Protocol Exceptions to Expedited Reporting (SPEER)
Likely (>20%)	Less Likely (<=20%)	Rare but Serious (<3%)	
BLOOD AND LYMPHATIC SYSTEM DISORDERS			
	Anemia		Anemia (Gr 2)
CARDIAC DISORDERS			
		Cardiac arrest	
		Ventricular fibrillation	
GASTROINTESTINAL DISORDERS			
	Abdominal pain		Abdominal pain (Gr 2)
	Constipation		Constipation (Gr 2)
Diarrhea			Diarrhea (Gr 2)
	Dry mouth		Dry mouth (Gr 2)
Mucositis oral			Mucositis oral (Gr 2)
Nausea			Nausea (Gr 2)
Vomiting			Vomiting (Gr 2)
GENERAL DISORDERS AND ADMINISTRATION SITE CONDITIONS			
	Edema limbs		
Fatigue			Fatigue (Gr 2)
	Fever		Fever (Gr 2)
	General disorders and administration site conditions - Other (mucosal inflammation)		General disorders and administration site conditions - Other (mucosal inflammation) (Gr 2)
INFECTIONS AND INFESTATIONS			
	Urinary tract infection		Urinary tract infection (Gr 2)
INVESTIGATIONS			
	Creatinine increased		Creatinine increased (Gr 2)

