		Electrocardiogram QT corrected interval prolonged	
	Platelet count decreased		Platelet count decreased (Gr 2)
	Weight loss		Weight loss (Gr 2)
METABOLISM AND NUTRITION DISORDERS			

Anorexia			Anorexia (Gr 2)
	Dehydration		Dehydration (Gr 2)
Hyperglycemia			Hyperglycemia (Gr 2)
	Hypokalemia		Hypokalemia (Gr 2)
	Hypomagnesemia		Hypomagnesemia (Gr 2)
	Hypophosphatemia		Hypophosphatemia (Gr 2)
MUSCULOSKELETAL AND CONNECTIVE TISSUE DISORDERS			
	Arthralgia		
	Back pain		Back pain (Gr 2)
	Pain in extremity		
NERVOUS SYSTEM DISORDERS			
	Dizziness		Dizziness (Gr 2)
	Dysgeusia		Dysgeusia (Gr 2)
	Headache		Headache (Gr 2)
PSYCHIATRIC DISORDERS			
	Insomnia		
RESPIRATORY, THORACIC AND MEDIASTINAL DISORDERS			
	Cough		Cough (Gr 2)
	Dyspnea		Dyspnea (Gr 2)
		Pneumonitis	
	Respiratory, thoracic and mediastinal disorders - Other (oropharyngeal pain)		
SKIN AND SUBCUTANEOUS TISSUE DISORDERS			
Pruritus			Pruritus (Gr 2)
Rash maculo-papular			Rash maculo-papular (Gr 2)

¹This table will be updated as the toxicity profile of the agent is revised. Updates will be distributed to all Principal Investigators at the time of revision. The current version can be obtained by contacting [contact]. Your name, the name of the investigator, the protocol and the agent should be included in the e-mail.

Adverse events reported on MLN0128 (TAK228) trials, but for which there is insufficient evidence to suggest that there was a reasonable possibility that MLN0128 (TAK228) caused the adverse event:

Cardiac disorders - Heart failure; Pericardial effusion; Sinus tachycardia

Eye disorders - Blurred vision; Eye disorders - Other (visual acuity reduced); Eye pain; Photophobia

Gastrointestinal disorders - Dyspepsia; Dysphagia; Esophagitis; Gastroesophageal reflux disease; Gastrointestinal disorders - Other (intestinal obstruction); Oral pain; Pancreatitis; Small intestinal obstruction; Small intestinal perforation; Toothache

General disorders and administration site conditions - Chills; Gait disturbance; Non-cardiac chest pain; Pain

Hepatobiliary disorders - Gallbladder obstruction

IMMUNE SYSTEM DISORDERS - Allergic reaction

Infections and infestations - Kidney infection; Lung infection; Sepsis; Skin infection; Upper respiratory infection

Injury, poisoning and procedural complications - Fall; Tracheal obstruction

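### Hypomagnesemia is a listed possible drug effect and counts under the safety rules, but it is the only such electrolyte term with no matching analyte in the chemistry panel

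*Combined protocol and SAP*

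**What the plan says.** Footnote a of the Study Calendar (Section 10) defines the chemistry panel in full: "Albumin, alkaline phosphatase, total bilirubin, bicarbonate, BUN, calcium, chloride, creatinine, fasting glucose, LDH, phosphorus, potassium, total protein, SGOT [AST], SGPT [ALT], sodium, uric acid".

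The CAEPR in Section 7.1.1 places hypokalemia, hypomagnesemia and hypophosphatemia in its possible-relationship table, all in the Less Likely column (20% or below). Each has a grade 2 entry in the SPEER column; the magnesium entry begins "Hypomagnesemia (Gr 2". The instruction for that column is "Report AEs on the SPEER ONLY IF they exceed the grade noted in parentheses".

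Three other rules take electrolyte events as input:

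- Section 6 covers "Non-hematological toxicities of fatigue, electrolyte abnormalities and abnormal liver function tests" and requires dose modification only if the event is likely or definitely related and lasts more than 7 days. It names no electrolyte.
- Section 13.5.2 counts as a DLT any related grade 4 non-hematological toxicity, and any related grade 3 one that has not fallen below grade 3 within 3 days. The only laboratory values given a different time limit are bilirubin, AST, ALT and alkaline phosphatase.
- Section 13.6.1 suspends accrual on related grade 4 non-hematological events. It sets aside potassium, low calcium, high urate and low phosphate abnormalities that resolve within 7 days. Magnesium is not in that list.

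The same CAEPR lists "Electrocardiogram QT corrected interval prolonged", "Ventricular fibrillation" and "Cardiac arrest" as rare but serious.

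**The concern.** A laboratory-defined adverse event enters the data only if someone orders the test. The plan sets thresholds for hypomagnesemia, but the one chemistry panel it spells out does not produce the value. Sites that add magnesium by habit would record events, and sites that do not would record none, so the observed rate would partly reflect local ordering practice.

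This affects the maximum-grade tables of Section 13.4.5 and, in principle, the two small-number safety decisions. The initial safety cohort turns on 2 or more DLTs in 6 patients (13.5.1), and the stopping rule on 3 or more grade 4 events in the first 12 (13.6.1). Under the first of these, a single DLT that is not seen matters if exactly one other DLT has been observed.

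**Working it through.** The plan gives no figure to reproduce. The check sets the risk list, the panel and the rules side by side.

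**Step 1. Electrolyte terms in Section 7.1.1 against footnote a.**

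| CAEPR term | Standing in the CAEPR | Analyte in footnote a |
|---|---|---|
| Hypokalemia | possibly related, SPEER grade 2 | potassium |
| Hypophosphatemia | possibly related, SPEER grade 2 | phosphorus |
| Hypomagnesemia | possibly related, SPEER grade 2 | none |
| Hypercalcemia, hypocalcemia | reported, insufficient evidence of causation | calcium |
| Hyponatremia | reported, insufficient evidence of causation | sodium |

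Magnesium is the only gap: 1 of 3 among the possibly related terms and 0 of 3 among those with insufficient evidence. The panel covers electrolytes less closely tied to the drug and leaves out one that is tied to it. No reason is given.

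**Step 2. What each rule needs.**

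| Rule | Does hypomagnesemia count? | Input needed |
|---|---|---|
| SPEER, 7.1.1 | yes, above grade 2 | a graded value |
| Section 6, electrolytes | yes, if likely or definitely related | values spanning more than 7 days |
| DLT, 13.5.2 | yes, no exemption | a grade, and for grade 3 a repeat within 3 days |
| Stopping rule, 13.6.1 | yes, not among the excluded abnormalities | a grade 4 value |

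The SPEER only says how to handle an event once it is known; it sets no testing schedule. The Section 6 and DLT rules contain a duration, so a single chance measurement would not settle them.

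**Step 3. Can the effect be sized?** Two bounds are available, and neither is an estimate.

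- All grades: the Less Likely column is capped at 20%. The ceilings are 0.20 × 26 = 5.2 evaluable patients and 0.20 × 35 = 7.0 accrued patients. These bound how many patients might have the event, not how many events would be missed.
- Grade 3 or higher: Section 2.2.3 lists the terms reported in 6% or more of 142 patients in the solid-tumor study. Hypomagnesemia is not among them, so its reported rate there was below 6%. In a cohort of 6 that is fewer than 0.06 × 6 = 0.36 expected events, before requiring drug-relatedness and, for grade 3, failure to resolve within 3 days. That study used other doses and schedules, and the documents do not say how often it measured magnesium.

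**Step 4. Efficacy design.** The CR/CRi endpoint, the 26-patient decision rule, the 0.09 significance level and the 0.85 power at a 30% success rate use no electrolyte data and do not change.

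**The case against.** The strongest reply is that the calendar grid is mostly unreadable. One single-site research-blood row and the footnotes remain. Footnote a defines one chemistry panel, not every laboratory test. Other items the protocol plainly needs, such as HbA1C (3.1.7), the white cell count (3.2.2) and the ECG for QTc (3.2.9), are also missing from what can be read of the calendar. This stands. A reader might infer that magnesium is not monitored at all, and the documents do not support that. What remains is that the panel holding the other electrolytes is listed in full without magnesium, and that no surviving footnote or other readable text asks for it.

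A reader might also infer that the electrolyte rule cannot be applied to magnesium. That is wrong. Section 6 names no analyte, so it applies to any magnesium value a site obtains, and Section 7.4 requires every adverse event to be reported. The gap is in systematic detection.

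A third tempting inference joins low magnesium to the cardiac risk, because Section 2.2.3 states that "A death on INK128-001 due to ventricular arrhythmia and cardiac arrest was assessed as possibly related to MLN0128 (TAK-228"). The documents list these events separately from hypomagnesemia, state no link, and do not attribute the death to magnesium. The same section goes on to report a dedicated QT study (a single 40 mg dose, then 30 mg weekly) with no clinically meaningful electrocardiographic effect, and an agreement on ECGs before entry, at completion and periodically when appropriate. The cardiac terms are co-listed and no more.

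**Conclusion.** The mismatch is real: a listed possible drug effect, counted by four rules, has no matching analyte in the enumerated panel. If no separate magnesium row exists, ascertainment is left to each site and may be uneven or incomplete.

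The size cannot be stated from the documents. Reading the ceilings of 5 in 26 or 7 in 35 as missed events would treat a category limit as a rate and assume that no site ever measures magnesium. An understated DLT count is possible but not shown: the reported grade 3 or higher rate in the solid-tumor study was below 6%, and no effect on the 2-of-6 decision is demonstrated.

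The conclusion rests on two assumptions: that the unreadable part of the calendar holds no magnesium row, and that local ordering varies between sites. This is a safety-ascertainment point and does not bear on the primary endpoint.

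**What to change.** First check the full calendar grid. If magnesium already has its own row, no change to testing is needed, and a cross-reference in footnote a would settle the point. If it does not, add magnesium to the footnote a panel on the same schedule as potassium and phosphorus, so that all three possibly related electrolyte terms are measured alike and feed Sections 6, 7.1.1, 13.5.2 and 13.6.1. If the sponsor prefers to leave it out, the protocol should say why.

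The cost is one analyte on a sample already drawn, with no new visit or procedure, plus some additional low-grade laboratory adverse events to record. No dose, dose-modification rule or stopping rule changes. The change gives magnesium parity with the other two. Whether the shared schedule is frequent enough for the 3-day and 7-day conditions cannot be judged from the readable calendar.
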